The purpose of the current study is to develop an evidence-based, health-promoting intervention and investigate its effects on well-being and mental health among school pupils aged 10 to 16 in Moss municipality, Norway.

In the first phase of the study, we will pilot the intervention at two selected schools in Råde municipality. In the second phase of the study, we will run a full-scale trial at the public schools in Moss (16 schools; approximately 3,300 pupils). For the latter purpose, we will use the quasi-experimental Extended Selection Cohorts design. We will investigate the changes in the pupils' scores on health behaviours, mental health, and well-being from baseline to different timepoints of data collection during a 12 months follow-up period.

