2.2 Objectives

Our objectives are:

1. To adapt the existing *Five ways to wellbeing* course for adults to a school setting, and to pilot the intervention in two schools.
2. To explore how participating pupils, teachers, and other school personnel experience the pilot intervention, and identify aspects that should be adjusted before proceeding to a full scale trial.
3. To examine how the teachers deliver the intervention in the full scale trial; their motivation, obstacles they encounter, general satisfaction with the intervention, and their adherence to the intervention manual (i.e., fidelity).
4. To investigate whether the intervention is acceptable and experienced as useful for participating school pupils, parents, teachers, and other school personnel.
5. To investigate whether the intervention have any adverse effects, such as triggering negative emotions.
6. To evaluate the process of implementation.
7. To describe the pupils' wellbeing and mental health at baseline (November 2023).

8. To examine the immediate and long-term effects of the intervention on the pupils' wellbeing and mental health.
9. To assess for whom the intervention is effective (i.e., subgroup analysis and moderation analysis, for example SES, gender, baseline symptom levels, etc.).
10. To investigate what mechanisms explain potential improvements in wellbeing after exposure to the interventions.

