2.3 Trial design

In phase 1, we will conduct a pilot study in two chosen schools in Råde Municipality.

In phase 2, we will use the quasi-experimental Extended Selection Cohorts (ESC) design. The ESC design is an option for real-life settings when an RCT is not feasible, because the ESC design makes it possible to compare same-age treatment groups. For the current study, a cluster-RCT of sufficient power would have needed a large number of schools and is therefore not feasible. The ESC design is a cohort-longitudinal design with adjacent cohorts, that are measured at two or more time points; a design that has been used to evaluate effects of school-based interventions, for example anti-bullying programmes (Kärnä et al., 2011; Olweus, 2005) and a programme that promotes physical activity and a healthy diet (Takens et al., 2020). Each cohort comprises subjects of approximately the same age. In a standard RCT design, the pupils, classes, or schools are randomly allocated to different intervention and control groups; but in the ESC design intervention and control groups belong to the same schools, and fewer schools or pupils are therefore needed. The cohorts that are exposed to the intervention are compared with unexposed cohorts from the same school, ensuring that the research subjects are recruited from a relatively stable population with the same socio-demographic characteristics (Olweus, 2005; Takens et al., 2020). This is important when studying health and health behaviour, which differs according to different SES and ethnicity groups. The ESC design does not, however, allow us to control for general societal time trends that coincide with the intervention.

In our study, we will collect data from each cohort (i.e., school grade) five times, starting in November, 2023 (baseline), followed by January, February, March, and November, 2024.

At 12 months follow-up, each cohort will be compared to the same-age adjacent baseline cohort group (see Figure 1). For instance, the measures of the grade 5 cohorts that will have been *exposed* to the intervention (grade 5 in 2024–2025) will be compared to the baseline measures of the *unexposed* grade 5 cohorts (grade 5 in 2023–2024).

Figure 1. How exposed cohorts can be compared to unexposed cohorts at 12 months follow-up

	Cohort A	Cohort B	Cohort C	Cohort D	Cohort E	Cohort F
Baseline (Nov. 2023)	Grade 5	Grade 6	Grade 7	Grade 8	Grade 9	Grade 10
Intervention						

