Follow-up (Nov. 2024)	Grade 6	Grade 7	Grade 8	Grade 9	Grade 10	

In order to separate any effects of the intervention from changes in variables due to other causes, we will apply a «wait list control group» element, i.e., delayed intervention: approximately $\frac{1}{2}$ of the schools will start the intervention in November 2023, while the remaining schools will start the intervention approx. 14 weeks later. We will collect data from all pupils in November 2023, and in February 2024 we will compare the scores of the intervention group with the «wait list» group.

3 Methods

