3.7 Sample size

During the study period, there will be approximately 3,300 pupils in grade 5 to 10 in the public schools in Moss, who will be invited to participate. We have a conservative estimate of 70 % participation, i.e., about 2,300 participants. All pupils in 157 school classes in Moss municipality will be invited to participate in our study. The average number of pupils in a school class in Moss is 21, and we assume that 15 pupils per class (i.e., 70 %) participate.

Estimating statistical power in a clustered trial that is not randomized can be challenging, as we need to account for the correlation within clusters and the variation between clusters, as well as the variation in the outcome measure(s). Our approach to determine statistical power was to run a power analysis available at <http://psychstat.org/crt2arm> with the following assumptions:

- Sample size (i.e., number of participating pupils per class): 15
- Effect size: 0.16
- Number of clusters (i.e., number of school classes); 157
- Intra-class correlation: 0.05

- Significance level: 0.05
- Power curve: No power curve
- H1: Two-sided test

This analysis resulted in a power of 0.8411. The assumption that our intervention might have an effect size of 0.16 is based on previous studies, see (Tanner-Smith et al., 2018; Taylor et al., 2017; Werner-Seidler et al., 2017).

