3.11 Statistical Analysis Plan

To analyse the effect of the intervention we will use multilevel regression. In these analyses individual measurements at the five timepoints are nested within pupils (level 2), which in turn are nested within classes (level 3), in turn nested within schools (level 4). We will use linear multilevel regression for all continuous outcome measures, and logistic multilevel regression for categorical outcome variables.

Multilevel models are ideally suited for clustered and longitudinal data, where the common assumption of independence of measures does not hold. The models also perform well with missing data, and can be used to investigate both general trends, and factors underlying the variability observed at various levels in the hierarchy.

Based on previous research we hypothesize that the effects of the intervention will be greater for individuals who score lower on wellbeing measures and/or higher on mental health symptoms at baseline. We will therefore stratify our sample based on the participants' wellbeing scores and their mental health symptoms score and perform subgroup analysis. We also hypothesize that the effects of the intervention will be greater for younger participants, and we will therefore perform subgroup analysis based on school grade (as a proxy for participants' age).

To explore the moderation effects by SES, gender, age in years, ethnicity, baseline level of mental health symptoms, loneliness, wellbeing level, and leisure activities level, we will add interaction terms to the model. When these terms are significant, we will stratify the analyses for specific subgroups.

A significance level of $p = 0.05$ will be used. For the analyses we will use Stata v. 18, IBM SPSS Statistics v. 25.0, and R 3.5.3.

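### The baseline-severity subgroup and interaction analyses name no comparison, and in the 12-month same-grade comparison or in within-pupil change regression to the mean would make them invalid

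*Combined protocol and SAP*

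**What the plan says.** Section 3.11 hypothesises that effects will be "greater for individuals who score lower on wellbeing measures and/or higher on mental health symptoms at baseline". It plans strata on "wellbeing scores and their mental health symptoms score and perform subgroup analysis". For moderation it lists SES, gender, age and ethnicity together with "baseline level of mental health symptoms, loneliness, wellbeing level, and leisure activities level, we will add interaction terms to the model". A significant interaction leads to stratified analyses. The section defines no exposure term, comparison or timepoint for any of this.

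Three comparisons are described elsewhere:

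- **Wait-list comparison, section 2.3:** "in February 2024 we will compare the scores of the intervention group with the" wait-list schools. Both groups have a November 2023 score.
- **Same-grade comparison, section 2.3:** "At 12 months follow-up, each cohort will be compared to the same-age adjacent baseline cohort group".
- **Within-pupil change, section 2.1:** changes in pupils' scores "from baseline to different timepoints of data collection during a 12 months follow-up period".

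Objective 8 in section 2.2 is "To examine the immediate and long-term effects of the intervention", and objective 9 asks for whom the intervention works, with no time limit. No section ties the severity analyses to one comparison, and regression to the mean is not mentioned.

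**The concern.** Both school groups receive the programme during the 2023–24 school year, so in November 2024 there is no concurrent unexposed group. Any long-term analysis by baseline severity must therefore use the same-grade comparison or within-pupil change.

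In the same-grade comparison the unexposed outcome is the November 2023 score. That is the first wave, so no earlier score exists to stratify on, and splitting these pupils by baseline means selecting them on the outcome itself. Exposed pupils are selected on a score taken a year before their outcome. Low scorers on the exposed side have had a year to regress upward, while low scorers on the unexposed side have not. Within-pupil change has no unexposed comparator at all, so regression cannot be separated from a larger effect. Random effects for pupil, class and school do not help, and nor does the interaction term, because the fault lies in what is compared.

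At stake is a confident false confirmation of the plan's own hypothesis under objective 9.

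**Working it through.** **The plan's own figure.** Section 3.7 gives 157 classes, 15 pupils per class, ICC 0.05, effect 0.16 and "Significance level: 0.05", two-sided. The noncentrality is 0.16 × √(157 / (4 × (0.05 + 0.95/15))) = 2.978. With 155 degrees of freedom the power is 0.8411, as stated. That figure concerns the overall effect. It is used here only for the 0.16 benchmark and the cluster structure.

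**Assumptions.** Scores are standard normal, with higher meaning better. The true effect is zero. The split is at the lowest third, since section 3.11 gives no cut-off. The 12-month correlation r runs from 0.4 to 0.8, since the documents give none.

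**Same measure as stratifier and outcome, both sides split.** The mean of the lowest third of a standard normal is −1.091. Exposed low scorers average −1.091r at follow-up, and unexposed low scorers average −1.091. The false gain is 1.091 × (1 − r):

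| r | False gain, lowest third (SD) | False interaction per SD of baseline (r − 1) |
|---|---|---|
| 0.4 | 0.654 | −0.6 |
| 0.5 | 0.545 | −0.5 |
| 0.6 | 0.436 | −0.4 |
| 0.7 | 0.327 | −0.3 |
| 0.8 | 0.218 | −0.2 |

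The interaction follows because the slope of outcome on baseline is 1 in unexposed pupils and r in exposed pupils. The highest third shows the mirror image, a false loss. The gain exceeds 0.16 whenever r < 1 − 0.16/1.091 = 0.85.

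**Within-pupil change.** The expected change in the lowest third is −1.091r + 1.091, the same quantity.

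**Only exposed pupils split, compared with the whole unexposed grade.** The difference is −1.091r, or −0.44 to −0.87 SD. This is a false harm.

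**Stratifier and outcome are different measures.** The bias is 1.091 × c × (1 − k), where c is the concurrent correlation and k the share of it retained at 12 months. With assumed c of 0.3 to 0.6 and k of 0.6 to 0.8, it runs from 1.091 × 0.3 × 0.2 = 0.07 to 1.091 × 0.6 × 0.4 = 0.26 SD.

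**Simulation of the 12-month comparison, zero effect** (157 classes of 15, ICC 0.05, five same-grade pairs). The low-third difference was 0.654, 0.432 and 0.219 at r = 0.4, 0.6 and 0.8, with empirical SE 0.047, 0.039 and 0.031. With 20% attrition it was 0.656, 0.430 and 0.218 (SE 0.049, 0.043 and 0.033). The overall comparison stayed within 0.005 of zero. In a simpler run without clustering (1,000 replicates, 1,150 pupils per group), the false interaction was significant at 0.05 in every replicate.

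**Wait-list comparison, zero effect.** In the simpler run the low-third difference was 0.00, and the interaction was rejected in 4.2% to 6.1% of replicates, close to nominal. A run with 16 schools, 8 per group, and an assumed November–February correlation of 0.5 to 0.8 gave a low-third difference within 0.005 of zero. If the school groups differ by 0.1 SD at the outset, the low-third difference is falsely 0.04 to 0.06 SD, but the interaction stays at 0.00.

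**The case against.** The strongest reply is that the error is conditional. No section says severity strata will be applied to the same-grade comparison. A model of five timepoints within pupils can be read as early-start versus delayed-start schools over time, and section 2.1 states a purpose rather than an estimator. It is true that the plan does not commit itself to an invalid version. But it does not exclude one, and a long-term version has no other comparison to use.

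The five-timepoint reading is not safe either if November stays in the model as an outcome. Take one early-start and one delayed-start pupil, with delayed-start pupils unexposed in January and February. Their unexposed occasions have slopes 1, 1, r and r on baseline, and all exposed occasions have slope r. Weighted equally, the false interaction is r − (1 + r)/2, or −0.20 per SD at r = 0.6. It vanishes once November is only a covariate.

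A second reply is that delayed-start pupils' February score could serve as the unexposed outcome, stratified on November. The bias would then be 1.091 × (3-month minus 12-month correlation), for example 1.091 × (0.7 − 0.6) = 0.11 SD. That is smaller but not zero, and it is not the comparison section 2.3 describes.

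Third, the size rests on assumptions. The correlation and the cut-off are not in the documents. A four-point loneliness item and a 0–10 ladder are not normal, and no separate figure is available for leisure activities. This stands as a caution on exact values. Only r = 1 removes the same-measure bias.

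Fourth, a 12-month split labelled descriptive would be milder than excluding it. That is so, but the resulting number could not be interpreted as effect modification.

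**Conclusion.** The concern holds. Section 3.11 names no comparison for the baseline-severity analyses, and two of the three that the protocol describes would give a wrong answer by construction. When stratifier and outcome are the same measure and both sides are split, the false gain in the lowest third is 0.22 to 0.65 SD for assumed r of 0.8 down to 0.4, against a planned effect of 0.16. With different measures it is about 0.07 to 0.26 SD, so sometimes below 0.16. When both sides are split, the error points the way the plan hypothesises.

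The problem is confined to moderators that are baseline self-reported scores related to the outcome. It does not touch gender, grade, SES or ethnicity, or the overall February and 12-month comparisons. The wait-list comparison is sound for this purpose as long as the two school groups are comparable, which cannot be taken for granted because no randomisation is stated. This should be fixed before analysis.

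**What to change.** Add to section 3.11:

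> Moderation by baseline self-reported scores (wellbeing, mental health symptoms, loneliness, leisure activities) will be tested only in the concurrent comparison of November-start and wait-list schools in February 2024 (January 2024 supportive), with a group-by-continuous-baseline interaction in the multilevel model, adjusted for the baseline score. The November 2023 score enters as a covariate and not as an outcome. Neither the 12-month same-grade comparison nor within-pupil change will be split by any of these scores. Moderators at 12 months are limited to SES, gender, grade and ethnicity.

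Also state that equal regression to the mean in the two groups assumes comparable school groups, report baseline means by group, and base the conclusion on the interaction term rather than on stratum-specific differences.

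The change needs no new data. It gives up a 12-month estimate by baseline severity. The February test remains informative. Its simulated interaction SE is 0.024 to 0.038 per SD of baseline, or 0.040 to 0.044 with an assumed between-school slope SD of 0.05. At 80% power (2.80 × SE) the detectable interaction is about 0.07 to 0.12 per SD. With a t multiplier on 14 degrees of freedom (about 3.01) the upper end is about 0.13.

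The model needs school, class and start-group codes. Section 4.5 removes school and class from the final dataset. That conflict already affects the model in section 3.11 and should be reconciled in the same revision.

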3.4.7 Other demographics

Gender will be assessed. Only school grade (grades 5 to 10) but not age will be assessed. In the Norwegian school system, attendance in school grades is strictly organized by birth cohorts, and staying back (repeating a grade) due to poor academic performance is generally not practised. We therefore use school grade as an indicator of age.

The pupils will be asked whether both their parents are born in a country other than Norway, and whether they have one or two homes.

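### The planned age interaction names a variable that is not collected, and the hypothesis of larger effects in younger pupils is tied to grade subgroups without a named test of whether effects differ

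*Combined protocol and SAP*

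**What the plan says.** Section 3.11 deals with age in two places.

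- **The hypothesis.** The plan states: "We also hypothesize that the effects of the intervention will be greater for younger participants". The analysis that follows from it is "we will therefore perform subgroup analysis based on school grade", with grade described as a proxy for age. The sentence names no comparison between grades and sets no condition for doing the subgroup analysis.
- **The moderators.** The next paragraph begins "To explore the moderation effects by SES, gender, age in years, ethnicity" and ends its list with "leisure activities level, we will add interaction terms to the model". It adds: "When these terms are significant, we will stratify the analyses for specific subgroups". School grade is not among the listed moderators.

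Section 3.4.7 states "Only school grade (grades 5 to 10) but not age will be assessed" and, after explaining that Norwegian grades follow birth cohorts, "We therefore use school grade as an indicator of age". Section 4.5 keeps school grade in the final dataset.

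**The concern.** The moderator list names a variable that will not exist in the data. The age hypothesis is paired, as written, with a stratified analysis only. An effect that is significant in one stratum and not in another is not evidence that the effects differ. With small strata, such a pattern is likely to arise by chance when the effect is the same everywhere.

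At stake is the age part of Objective 9, which asks for whom the intervention is effective. If the test is not fixed in advance, several choices can be made after the data are seen: single grades or bands, linear or categorical coding, and whether the interaction or the strata decide the claim.

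**Working it through.** **Inputs (section 3.7):** J = 157 classes, n = 15 pupils per class, effect d = 0.16 SD, intra-class correlation ρ = 0.05, two-sided α = 0.05.

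**Assumptions added here:** classes spread evenly over six grades, the two-arm set-up of section 3.7 with class as the only cluster level, and independent results across strata.

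**1. The plan's own figure.** Noncentrality λ = √[J·d² / (4ρ + 4(1−ρ)/n)].
- The denominator is 4(0.05) + 4(0.95)/15 = 0.4533.
- λ = √(157 × 0.0256 / 0.4533) = 2.978.
- The noncentral t with 155 df gives power 0.8411, which matches section 3.7 exactly.
- The standard error of the overall effect is 0.16/2.978 = 0.0537 SD.

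**2. Power within strata, if the true effect is 0.16 SD in every grade.**
- Single grade: 157/6 ≈ 26.2 classes, λ = √(26.17 × 0.0256 / 0.4533) = 1.216, power ≈ 0.21.
- Three-grade band: 157/2 = 78.5 classes, λ = √(78.5 × 0.0256 / 0.4533) = 2.106, power ≈ 0.55.

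**3. Chance of a mixed pattern when effects do not differ.**
- Six grades: 1 − 0.215⁶ − 0.785⁶ ≈ 0.77. The expected number of significant grades is 6 × 0.215 ≈ 1.3.
- Two bands: 2 × 0.547 × 0.453 ≈ 0.50.

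**4. Chance of at least one significant stratum when there is no effect anywhere.**
- Six tests: 1 − 0.95⁶ ≈ 0.26.
- Two tests: 1 − 0.95² ≈ 0.10.

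**5. Precision of a direct test, on the same assumptions.**
- Linear trend: the SD of grade, uniform over six values, is √(35/12) = 1.708. The SE of the trend is 0.0537/1.708 = 0.0315 SD per grade. The trend detectable with 80% power is (1.960 + 0.842) × 0.0315 ≈ 0.088 SD per grade, or about 5 × 0.088 = 0.44 SD from grade 5 to grade 10.
- Grades 5–7 against 8–10: the SE of the difference in effects is 2 × 0.0537 = 0.107 SD. The detectable difference is 2.802 × 0.107 ≈ 0.30 SD.

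**The case against.** **The interaction is available.** A reader might infer that the age interaction cannot be run, or that the hypothesis has no valid test. The documents do not support that. Section 3.4.7 makes grade the study's indicator of age, section 3.11 calls it a proxy, and section 4.5 keeps it in the dataset. Reading the planned age interaction as a grade interaction is natural. This stands, and it reduces the point to a wrong variable name and an unspecified test. It does not remove the point, because the plan neither lists grade as a moderator, nor gives its coding, nor says that the interaction decides the hypothesis.

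**The plan does not say it will count significant grades.** This is correct. For the listed moderators it takes the sounder order of interaction first and strata afterwards. The grade subgroup analysis, however, comes before that rule and is not made subject to it.

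**Six single-grade tests are an assumption.** This also stands. The plan says only that subgroups are based on grade, and bands are possible: the teacher questionnaire in section 3.4.9 itself separates grades 5–7 from 8–10. As drawn, Figure 1 gives five same-grade contrasts at 12 months, for which the chance in step 4 would be 1 − 0.95⁵ ≈ 0.23. The figures therefore form a range.

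**The power figures are simplified.** Section 3.11 plans five repeated measurements and a school level, and section 2.3 staggers the start by school. These features could move power in either direction. Step 4 also concerns false positives under no effect at all, which is not the error rate of a test for differing effects.

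**Objective 9 is wider than age.** A reader might infer that the whole objective would be answered from a pattern of significant grades. It would not: the interaction terms for SES, gender, baseline symptoms and the other listed factors are untouched.

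**Conclusion.** The point holds as a minor matter of specification. The SAP names age in years as a moderator although only grade is assessed, and it does not name the test of its hypothesis about younger pupils. A valid test can be made with data already planned.

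If the strata were read in place of that test, a uniform effect of 0.16 SD would give a misleading mixed pattern with probability of about 0.50 (two bands) to 0.77 (six grades). With no effect anywhere, at least one stratum would be significant with probability of about 0.10 to 0.26. These are illustrations that depend on the assumptions listed in the working; they are not predictions for the planned multilevel model.

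**What to change.** Amend section 3.11 as follows.

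- In the moderator list, replace age in years with school grade at baseline, coded as a linear term.
- State that the single exposure-by-grade interaction is the test of the hypothesis about younger pupils.
- Report grade-specific or grade-band estimates with confidence intervals as description only, and base any age-subgroup claim on the interaction.
- For the 12-month comparison, say which grade enters the term. In Figure 1, exposed and unexposed pupils compared in the same grade were one grade apart at baseline.

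This needs little more than one SAP sentence and no new data. It will yield fewer subgroup claims. The plan should also acknowledge the limited precision: a detectable trend of about 0.088 SD per grade is steep beside an assumed overall effect of 0.16 SD, so a non-significant interaction should not be read as showing equal effects across grades.

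### Five of the eight moderators get subgroup effects only if their interaction passes an unadjusted 0.05 test, so the subgroup differences displayed will be selected and exaggerated

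*Combined protocol and SAP*

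**What the plan says.** Objective 9 in section 2.2 is: "To assess for whom the intervention is effective (i.e., subgroup analysis and moderation analysis, for example SES, gender, baseline symptom levels, etc". Section 3.11 serves it by two routes.

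- **Unconditional route.** Larger effects are hypothesised for pupils with lower wellbeing or more symptoms at baseline, and for younger pupils. The plan commits to the matching analyses without any test: "We will therefore stratify our sample based on the participants' wellbeing scores and their mental health symptoms score and perform subgroup analysis", and "we will therefore perform subgroup analysis based on school grade (as a proxy for participants' age".
- **Conditional route.** The next paragraph reads "To explore the moderation effects by SES, gender, age in years, ethnicity, baseline level of mental health symptoms, loneliness, wellbeing level, and leisure activities level", and says that interaction terms will be added to the model. It then sets the rule: "When these terms are significant, we will stratify the analyses for specific subgroups".

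The threshold is general: "A significance level of $p = 0.05$ will be used". The models apply to every outcome: "We will use linear multilevel regression for all continuous outcome measures, and logistic multilevel regression for categorical outcome variables". Section 3.11 gives no multiplicity adjustment and no ranking of outcomes for these tests. It does not commit to reporting all interaction estimates, and it does not say that any will be withheld.

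**The concern.** Using a significance test to decide which subgroup effects to produce does two things. It lets chance findings through at a rate that grows with the number of tests. It also keeps an estimate only when it is large relative to its error, so the differences that appear are biased away from zero even when the moderator is real. Naming a single primary outcome would limit the first problem but not the second.

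Objective 9 asks for whom the programme works and names socio-economic status and gender as examples. Both depend on the trigger. A municipality deciding where to use the material could be guided by differences that look about twice as large as they are. For moderators that miss the threshold, the plan promises no subgroup estimates.

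**Working it through.** **Inputs.** Section 3.7: 157 classes, 15 pupils per class (157 × 15 = 2,355), intra-class correlation 0.05, effect size 0.16, two-sided 0.05. Section 3.11: eight moderators, three of which also have the unconditional route (age through school grade). The documents give no interaction size and no power for moderation, so those values below are assumptions.

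**1. The plan's own figure.** For a two-arm comparison of classes, the standard error of the main effect is sqrt(4 × (0.05 + 0.95/15)/157) = 0.0537. The noncentrality is 0.16/0.0537 = 2.978 and, with 155 degrees of freedom, power is 0.8411, as stated in section 3.7. The inputs are therefore read as the plan uses them.

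**2. False triggers, one outcome, no real moderator.**
- Five moderators that depend on the trigger alone: 1 − 0.95^5 = 0.226 (expected number 5 × 0.05 = 0.25).
- All eight interaction tests: 1 − 0.95^8 = 0.337 (expected number 8 × 0.05 = 0.40).
- These assume independent tests. With a common correlation of 0.3 or 0.5 between normal test statistics (assumed), the eight-test figure falls to 0.30 or 0.25, and the five-test figure to 0.21 or 0.18.

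**3. Standard error of an interaction.** Take a balanced two-level moderator that varies within classes, with no variation in its slope between classes. The class effect cancels, leaving residual variance 0.95:

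SE = 2 × sqrt(4 × 0.95/2,355) = 0.080 SD.

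This uses one measurement per pupil. If baseline adjustment is available, with an assumed correlation r between baseline and follow-up, SE is multiplied by sqrt(1 − r²): 0.070 at r = 0.5 and 0.057 at r = 0.7. The range 0.057 to 0.080 is carried forward. An unbalanced moderator would have a larger SE.

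**4. Exaggeration after selection.** With the estimate normal around the true value, compute the mean absolute estimate given that it exceeds 1.96 × SE, and divide by the truth.

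| True interaction (SD) | SE (SD) | Power | Mean significant estimate (SD) | Ratio to truth |
|---|---|---|---|---|
| 0.10 | 0.080 | 0.24 | 0.20 | 2.0 |
| 0.10 | 0.057 | 0.41 | 0.15 | 1.5 |
| 0.16 | 0.080 | 0.51 | 0.22 | 1.4 |
| 0.16 | 0.057 | 0.80 | 0.18 | 1.1 |
| 0.32 | 0.080 | 0.98 | 0.32 | 1.0 |

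The reason is visible in the threshold. At SE 0.080 nothing smaller than 1.96 × 0.080 = 0.157 SD can be significant, so a true 0.10 SD can never be displayed at its real size. The 0.16 SD rows are an interaction as large as the main effect assumed in section 3.7. The problem fades only when the true interaction is about twice that.

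**The case against.** Several points on the other side are sound.

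- **The trigger does not control all eight.** A reader might infer that subgroup effects appear only for moderators that reach significance. The paragraph before the rule contradicts this: baseline wellbeing, baseline symptoms and grade are stratified whatever any test shows. The point is confined to five moderators, and the matching false-trigger figure is 23%, not 34%.
- **Nothing in the text hides results.** A reader might infer that non-significant moderators will be suppressed. The rule conditions stratification, not the reporting of interaction terms, and all eight terms are to be fitted. Section 4.8 commits to open science practices and to statistical code on request. What is missing is an explicit commitment to tabulate every interaction.
- **Most displayed findings need not be false.** The 23% and 34% are chances of any false trigger when no moderator is real. The share of significant moderators that are false depends on how many are real and on power. If one of eight is real, it is 0.35/(0.35 + 0.50) = 41% at power 0.50 and 0.35/(0.35 + 0.25) = 58% at power 0.25. If three are real, it is 0.25/(0.25 + 1.50) = 14% and 0.25/(0.25 + 0.75) = 25%. The documents do not say which case applies.
- **The size of the exaggeration is conditional.** It rests on assumed interaction sizes and on a balanced split, which suits gender better than the 0–9 affluence scale or the four-point loneliness item.
- **The step is introduced as exploration.** That lowers the weight of any claim. It does not remove selection bias, and exploratory results are the ones that most need a complete, unselected set of estimates.

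**Conclusion.** The point holds in limited form. The conditional rule in section 3.11 will produce selected and, on average, exaggerated subgroup differences for five moderators, two of which objective 9 names. Per outcome, the chance of at least one false trigger is about 23% for these five and 34% across all eight interaction tests, assuming independence and no real moderator. Exaggeration is about 1.5 to 2.0 times for a true interaction of 0.10 SD and 1.1 to 1.4 times for 0.16 SD, assuming a balanced pupil-level moderator and an SE of 0.057 to 0.080 SD. It is negligible for interactions near 0.32 SD. The documents do not support saying that the other moderators' results will be concealed, or that most reported moderators will be false. The main effect analysis is not affected. The change should be made before the moderation analyses are run.

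**What to change.** In section 3.11:

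1. Delete the sentence that makes stratification depend on a significant interaction.
2. State that, for every listed moderator and every analysed outcome, the report will give the interaction estimate and the model-based subgroup effects with 95% intervals, all from the one interaction model and whatever the p-value.
3. Name baseline wellbeing, baseline symptoms and school grade as the pre-specified moderation hypotheses, since section 3.11 already states a direction for each.
4. Label the other five moderators exploratory, with no claim resting on p < 0.05.
5. While editing, reconcile the listing of age in years as a moderator with section 3.4.7, which says that grade is recorded and age is not.

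Adjusting the threshold instead would be the weaker remedy. Bonferroni over eight tests (0.05/8 = 0.00625 each) brings the chance of any false trigger to 1 − (1 − 0.00625)^8 = 0.049, but at SE 0.080 it cuts power for a true 0.16 SD interaction from 0.51 to 0.23, and estimates would still be selected on significance.

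The cost is a few lines of plan text and one extra results table, with no new data. The downside is that fewer subgroup findings can be called significant.
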